## STATISTICAL ANALYSIS PLAN VERSION HISTORY

This Statistical Analysis Plan (SAP) was developed based on Roche SAP model document eMD: 01 May 2024 (SAP eMD\_v3.0) and 01 Aug 2024 (Ophtha SAP Template\_v1.0)

SAP Ve	rsion	Approval Date	Based on Protocol (Version, Approval Date)
1.0		see electronic date stamp on the last page of this document	Substudy Protocol V2, 02 Nov 2022

## LIST OF ABBREVIATIONS AND DEFINITIONS OF TERMS

Abbreviation or Term	Description
AE	adverse event
AESI	adverse event of special interest
APTC	Anti-Platelet Trialists' Collaboration
ATE	arterial thromboembolic event
BCVA	best-corrected visual acuity
CEC	corneal endothelial cells
CSR	Clinical Study Report
CST	central subfield thickness
CV	coefficient of variation
ECD	endothelial cell density
GCP	Good Clinical Practices
IOI	intraocular inflammation
HEX	hexagonal endothelial cells
MedDRA	Medical Dictionary for Regulatory Activities
nAMD	neovascular age-related macular degeneration
mITT	modified intent-to-treat
PMR	post-marketing requirement
PTI	personalized treatment interval
PT	preferred term
SAEs	serious adverse events
SAP	Statistical Analysis Plan
SMQs	standardized MedDRA queries
SOC	System Organ Class
USFDA	United States Food and Drug Administration

## 1. INTRODUCTION

This Statistical Analysis Plan (SAP) specifies the planned analyses for the corneal endothelium cell (CEC) substudy of the main Study GR42691.

The main Study GR42691 is a multicenter long-term extension study designed to evaluate the long-term safety and tolerability of intravitreal faricimab 6 mg administered at a personalized treatment interval (PTI) to patients with neovascular age-related macular degeneration (nAMD) who enrolled in and completed one of the Phase III studies, GR40306 and GR40844.

This substudy is designed to evaluate the impact on corneal endothelial cells in the study eyes of patients with nAMD receiving intravitreal faricimab (6 mg) to fulfill a United States Food and Drug Administration (USFDA) post-marketing requirement (PMR). Specifically, the U.S. FDA PMR is stated as "conduct a controlled trial to evaluate the corneal endothelial health of eyes treated with faricimab by monitoring the number/density of corneal endothelial cells using specular microscopy at baseline and over a period of at least one year in at least 100 patients receiving faricimab."

The corneal endothelium is a single layer of cells lining the posterior portion of the cornea that regulates the health and optical transparency of the cornea (Van den Bogerd et al. 2019). The structural and functional integrity of the corneal endothelium can be impacted by a variety of extrinsic and intrinsic factors, including genetics, race, age, corneal dystrophy, ocular trauma, intraocular surgery, ultraviolet radiation, and intraocular infection. Morphological changes in the corneal endothelium occur throughout life, including a significant decline in corneal endothelial cell density (ECD) and percentage of hexagonal cells with age (Bourne et al. 1997; Zavala et al. 2013).

Specular microscopy is an imaging modality that allows for direct assessment of the corneal ECD and morphology and is routinely used in the assessment of corneal endothelial cell health (Chaurasia and Vanathi 2021). Variables studied in the specular microscopy examination include ECD, percentage of hexagonal endothelial cells (HEX), and coefficient of variation (CV) of cell area and collectively allow the clinician to interpret the health status of the CECs (Chaurasia and Vanathi 2021). Human corneal endothelium consists of a monolayer of hexagonal cells situated in the posterior surface of the cornea (Schmedt et al. 2012) and healthy cornea has approximately 60% of HEX (Chaurasia and Vanathi 2021). The percentage of HEX decreases (pleomorphism) and the CV of cell area increases (polymegathism) with age and endothelial cell attrition due to various causes (Chaurasia and Vanathi 2021).

The purpose of this document is to provide details of the planned analyses. The analyses and endpoints specified in this document supersede the analysis plan described in the study protocol. Changes to the protocol-planned analyses are described in Section 4.8.

## 1.1 OBJECTIVES AND ENDPOINTS

This substudy will evaluate the impact of faricimab on corneal endothelial cells in patients with nAMD. Specific objectives and corresponding endpoints for this substudy are outlined below.

The primary objective for this substudy is to evaluate the impact of faricimab on corneal endothelial cell health on the basis of the following endpoints, as assessed by specular microscopy:

- Primary endpoint: Percent change in corneal endothelial cell density from baseline at Year 1 (defined as the earliest substudy visit closest to Week 52 occurring between Week 48 and Week 64) in the study eye as compared with the fellow eye
- Secondary endpoint: Percent change in corneal endothelial cell density from baseline at substudy midpoint (defined as the earliest substudy visit closest to Week 24 occurring between Week 20 and Week 28) in the study eye as compared with the fellow eye

## Exploratory endpoints:

- Percent change in the coefficient of variation of corneal endothelial cell area (standard deviation of the cell area/mean cell area) from baseline at substudy midpoint and Year 1 in the study eye as compared with the fellow eye
- Percent change of hexagonal endothelial cells from baseline at substudy midpoint and Year 1 in the study eye as compared with the fellow eye

#### 1.2 STUDY DESIGN

The main Study GR42691 (AVONELLE-X) is a multicenter long-term extension study designed to evaluate the long-term safety and tolerability of intravitreal faricimab 6 mg administered at a PTI to patients with nAMD who enrolled in and completed one of the Phase III studies, GR40306 and GR40844.

This substudy is designed to evaluate the impact of intravitreal faricimab 6 mg administered at a PTI on the health of the corneal endothelial cells in patients with nAMD. Fellow eyes of enrolled patients will be used as a comparator for corneal endothelial cell analyses. Prior and/or current administration of faricimab in the fellow eye is one of the exclusion criteria for this substudy (refer to protocol Section 4.1.2). During the substudy, the following therapies are prohibited:

- faricimab
- brolucizumab (Beovu®)
- bevacizumab (Avastin®)
- Port Delivery System implantation (Susvimo™)

Patients in the main Study GR42691 will be eligible to screen for participation in this substudy. During the substudy screening visit, eligibility to participate will be determined Faricimab—F. Hoffmann-La Roche Ltd

Statistical Analysis Plan GR42691 CEC Substudy

based on the inclusion and exclusion criteria for this substudy (refer to protocol Section 4.1). Study GR42691 patients are required to be willing to participate in the CEC substudy for at least 48 weeks and have at least their first CEC substudy visit while enrolled in the main Study GR42691.

Patients who do not meet the criteria for participation in this substudy (screen failure) may qualify for one re-screening opportunity (for a total of two screenings per patient) at the investigator's discretion. Patients are not required to re-sign the consent form if they are re-screened within 90 days after previously signing the consent form. The investigator will maintain a record of reasons for screen failure (refer to protocol Section 4.4.1).

Figure 1 presents an overview of the substudy design. A schedule of activities is provided in protocol Appendix 1.

Faricimab PTI Standard of care PRN Weeks 20 24 52 Scrn./ **D1** Study Eye: Faricimab 6 mg PTI Fellow Eye: Standard of Care PRN Substudy Midpoint Year 1 Data Collection Data Collection

Figure 1 Substudy Assessment Schema

D1=Day 1; PRN=pro renata (as needed); PTI=personalized treatment interval; Scrn=screening visit.

Substudy midpoint data collection timepoint is defined as the earliest substudy visit closest to Week 24 occurring between Week 20 and Week 28. Year 1 data collection timepoint is defined as the earliest substudy visit closest to Week 52 occurring between Week 48 and Week 64.

When possible, patients will follow the scheduled assessments per the main protocol (see main Study GR42691 protocol Appendix 1). However, for some patients, an additional visit may need to be scheduled in between main protocol visits for the substudy midpoint visit. Substudy patients will undergo specular microscopy imaging in both eyes to assess number/density of corneal endothelial cells at screening, substudy

midpoint, and Year 1 prior to the application of any topical ophthalmic anesthetic, tonometry, or any other study treatment.

Completion of the substudy may occur prior to or after main study completion. If the patient withdraws from the substudy only, then the patient may remain in the main Study GR42691.

If the patient withdraws from the main Study GR42691, then the patient will also be withdrawn from this substudy.

If the patient discontinues treatment but remains in the main Study GR42691 for followup, then the patient will remain in this substudy. All patients who remain in this substudy will be strongly encouraged to complete specular microscopy imaging at substudy midpoint and Year 1.

The end of this substudy is defined as the date when the last patient, last visit occurs. The end of the substudy is expected to occur approximately 48 weeks after the last substudy patient is enrolled.

## 1.2.1 Treatment Assignment and Masking

There is no additional treatment compared to the main Study GR42691.

## 1.2.2 Independent Review Facility

A central reading center with expertise in specular microscopy assessment provided sites with the specular microscopy manual and training materials for specified substudy corneal images. Before any substudy images are obtained, site personnel, test images, systems, and software (where applicable) are certified and validated by the reading center as specified in the corneal reading center manual. All specular microscopy images are obtained by trained site personnel at the study sites, forwarded to the central reading center for independent analysis and/or storage, and later transferred to the Sponsor.

## 1.2.3 Data Monitoring

Not applicable

## 2. STATISTICAL HYPOTHESES AND SAMPLE SIZE DETERMINATION

#### 2.1 STATISTICAL HYPOTHESES

No formal hypothesis testing is planned for this study.

The paired t-tests are planned for efficacy analyses for reference purposes and thus not considered formal. In general, the paired t-tests will compare the percent change from baseline between the study eye and fellow eye in each CEC parameter described in

Faricimab—F. Hoffmann-La Roche Ltd **Statistical Analysis Plan** GR42691 CEC Substudy

Section 4.2, Section 4.3 and Section 4.4, respectively in the specified groups. The test will be 2-sided, with the null hypothesis of no difference in percent change from baseline between the study eye and fellow eye in each patient. P-values and 95% confidence interval of the difference from the paired t-tests will be provided.

## 2.2 SAMPLE SIZE DETERMINATION

No formal sample size calculations were performed for this substudy. A total of 117 patients were enrolled in this substudy from the main Study GR42691.

## 3. ANALYSIS SETS

Similar to main study analysis, patients from Good Clinical Practices (GCP) non-compliance affected site will not be included in the analyses due to possible impact of the GCP non-compliance. Details about the non-compliance can be found in AVONELLE-X main study SAP Section 3 and main study Clinical Study Report (CSR).

The analysis sets for the purposes of analyses are defined in Table 1.

Table 1 Analysis Sets

Analysis Set	Description
mITT set	All enrolled participants who received at least one injection of faricimab in the study eye during this substudy (with patients at GCP non-compliance affected site excluded from the analyses).
Safety-Evaluable set	All enrolled participants who received at least one injection of faricimab in the study eye during this substudy (with patients at GCP non-compliance affected site excluded from the analyses).

mITT = modified intent-to-treat

In general, analyses will include observations collected from substudy screening through to substudy completion/discontinuation, regardless of previous parent study treatment assignment.

Specific data points to be included for each analysis will be described in Section 4.

## 4. STATISTICAL ANALYSES

The analyses described in this section are based on patients enrolled in this CEC substudy. The analysis will be performed at the same time of the final analysis of the main study (refer to main SAP of GR42691).

#### 4.1 GENERAL CONSIDERATIONS

Unless specified otherwise, efficacy analyses will be performed on the modified intent-to-treat (mITT) set. Safety analyses will be performed on safety-evaluable set.

For efficacy analyses specified in Section 4.2, Section 4.3 and Section 4.4, baseline will be defined as the screening/Day 1 CEC image taken date. Midpoint will be defined as Faricimab—F. Hoffmann-La Roche Ltd

Statistical Analysis Plan GR42691 CEC Substudy

1

Clinical Study Report: faricimab - F. Hoffmann-La Roche Ltd Protocol Number: GR42691 Report Number: 1135769

the earliest analysis substudy visit closest to Week 24 occurring between Week 20 and Week 28. Year 1 will be defined as the earliest substudy visit closest to Week 52 occurring between Week 48 and Week 68.

Descriptive summaries for continuous endpoints will include number of observations, arithmetic mean, standard deviation, 95% CI for mean, median, minimum, maximum, first quartile (Q1), and third quartile (Q3). Descriptive summaries for binary/categorical endpoints will include frequency and/or percentages.

Data (from both study eye and fellow eye) collected after the fellow eye use of the prohibited therapies (listed below) will be excluded from the efficacy analysis:

- faricimab
- brolucizumab (Beovu®)
- bevacizumab (Avastin®)
- Port Delivery System implantation (Susvimo™)

Missing data will not be imputed.

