## 4.2 PRIMARY EFFICACY ENDPOINT ANALYSIS

## 4.2.1 Definition of Primary Endpoint/Estimand

The primary efficacy endpoint is the percent change from baseline in study eye ECD value at Year 1.

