## 4.2.2 Main Analytical Approach for Primary Endpoint

Available corneal ECD values and percent change from baseline in ECD values will be summarized descriptively at baseline and at Year 1, for study and fellow eyes respectively.

In addition, the percent change in corneal ECD from baseline at Year 1 will be analyzed using the paired t-test comparing study and fellow eyes. P-value and 95% interval from the paired t-test will be provided.

Paired t-test will be performed among the subset of patients who had an interpretable baseline and Year 1 specular microscopic image in both eyes.

Paired t-test comparing study eyes and fellow eyes within each of the following subgroups will also be provided:

• Baseline age (<65,  $\ge 65$  to <75, and  $\ge 75$  years)

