#### 4.3 SECONDARY EFFICACY ENDPOINT ANALYSIS

The secondary efficacy endpoint is the percent change from baseline in study eye ECD value at midpoint. The secondary endpoint will be analyzed using the same analysis methods as the primary endpoint, as described in Section 4.2.

Faricimab—F. Hoffmann-La Roche Ltd

Statistical Analysis Plan GR42691 CEC Substudy

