## 4.4 EXPLORATORY EFFICACY ENDPOINT ANALYSIS

Exploratory endpoints include:

- Percent change in the coefficient of variation of corneal endothelial cell area (standard deviation of the cell area/mean cell area) from baseline at substudy midpoint and Year 1 in the study eye
- 2. Percent change of hexagonal endothelial cells from baseline at substudy midpoint and Year 1 in the study eye

Exploratory endpoints will be analyzed using the same analysis methods as the primary endpoint, as described in Section 4.2, with the exception that subgroup analyses will not be performed for exploratory endpoints.

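### Should study-eye values stay in the study-eye summaries after the fellow eye receives a prohibited therapy?

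*SAP*

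**What the plan says.** SAP Section 4.1 sets the rule for the efficacy analyses: "Data (from both study eye and fellow eye) collected after the fellow eye use of the prohibited therapies (listed below) will be excluded". It names four therapies and rules out imputation, so an excluded value is simply absent.

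SAP Section 4.2.2 has two parts. The available values "will be summarized descriptively at baseline and at Year 1, for study and fellow eyes respectively". The between-eye test has a stricter requirement: "Paired t-test will be performed among the subset of patients who had an interpretable baseline and Year 1 specular microscopic image in both eyes". Midpoint ECD follows the same scheme (Section 4.3: "The secondary endpoint will be analyzed using the same analysis methods as the primary endpoint, as described in Section 4.2"). So do CV and HEX, without the age subgroups (Section 4.4: "Exploratory endpoints will be analyzed using the same analysis methods as the primary endpoint, as described in Section 4.2").

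The endpoint is worded in two ways. SAP Section 4.2.1 says "The primary efficacy endpoint is the percent change from baseline in study eye ECD value at Year 1". SAP Section 1.1 and Protocol Section 2.1.1 both define it as the study-eye percent change compared with the fellow eye.

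Protocol Section 4.3.2 prohibits the four therapies in the fellow eye but does not say what happens to data collected after their use. Protocol Section 6.5 selects patients by image availability in both eyes. SAP Section 1 says that changes to the protocol's analyses are described in Section 4.8. That section lists five changes, and this rule is not among them.

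**The concern.** The rule appears to discard good data for no return. In the paired test the study-eye exclusion is redundant, because without a fellow-eye value there is no pair. Its only effect is on the separate study-eye summary, where a measured eye drops out because of something that happened to the other eye.

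Three features of the SAP make that look serious. Section 4.2.1 words the primary endpoint on the study eye alone. Section 2.1 plays down the tests: "The paired t-tests are planned for efficacy analyses for reference purposes and thus not considered formal". And the regulatory requirement quoted in SAP Section 1 is to "conduct a controlled trial to evaluate the corneal endothelial health of eyes treated with faricimab" in at least 100 patients, with 117 enrolled. Read together, these suggest that the study-eye summary is the real primary analysis and that each lost study eye counts against the target. A reader who relied on Section 4.8 to learn how the SAP departs from the protocol would not find the rule.

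**Working it through.** The documents give no power, standard deviation or formal sample size for this point, so there is no planned figure to reproduce. The check has four steps.

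**1. Effect on the paired tests.** For each patient the test uses D = S − F, the study-eye minus the fellow-eye percent change, and needs both. If F is excluded, D does not exist, whether or not S is kept. The set of pairs is therefore identical under both rules.

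- Overall tests: 3 parameters (ECD, CV, HEX) × 2 time points = 6.
- Age subgroup tests: ECD at 2 time points × 3 age bands = 6.
- Total 12, of which 0 change.

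A simulation of 1000 data sets (117 patients, 0 to 20 of them affected) gave the same number of pairs and the same p-value under both rules every time.

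**2. Effect on the study-eye summaries.** The summaries exposed are 3 parameters × 2 post-baseline time points = 6. Each affected patient with otherwise usable images lowers n by 1. Baseline values and values taken before the event stay in. The half-width of the 95% confidence interval for a mean, in SD units, is t(0.975, n − 1)/√n. The number affected, k, is not in the documents. The values below are assumptions, applied to a base of all 117 enrolled and to a base of 100.

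| Base | k | n kept | Half-width, all kept | Half-width, SAP rule | Ratio |
|---|---|---|---|---|---|
| 117 | 1 | 116 | 0.1831 | 0.1839 | 1.004 |
| 117 | 5 | 112 | 0.1831 | 0.1872 | 1.023 |
| 117 | 10 | 107 | 0.1831 | 0.1917 | 1.047 |
| 117 | 20 | 97 | 0.1831 | 0.2015 | 1.101 |
| 100 | 5 | 95 | 0.1984 | 0.2037 | 1.027 |
| 100 | 10 | 90 | 0.1984 | 0.2094 | 1.056 |
| 100 | 20 | 80 | 0.1984 | 0.2225 | 1.122 |

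Even 10 affected patients would widen the interval by only about 5% to 6%.

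**3. What the endpoint is.** SAP Section 4.2.1, read alone, is about one eye. SAP Section 1.1 and Protocol Section 2.1.1 include the comparison, and SAP Section 1.2 names the fellow eye as comparator. Protocol Section 3.3.3 gives the reason: endothelial cells change with age and differ widely between patients, so each patient's other eye is the control. The requirement itself asks for a controlled trial. SAP Section 2.1 says that the tests are not formal, but it still plans a 95% interval for the between-eye difference. On this reading a study-eye value without its control is supporting information.

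**4. The count of 100.** Enrolment exceeds 100 by 117 − 100 = 17. The requirement asks for monitoring in at least 100 treated patients, and Protocol Section 6.1 aims to obtain data from at least 100. Neither sets 100 as the minimum n of a study-eye table. A patient left out of that table under the rule was still treated and imaged.

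**The case for a change.** The best case for changing the rule is that the SAP gives no reason why treatment of one eye should invalidate a measurement in the other. The summaries already use available values for each eye, so the two columns can differ anyway through missing or unreadable images. A footnote could explain one more difference. Section 4.8 also drops the per-protocol analysis so that the study reflects real-world use, including non-adherence, and a deviation-based exclusion in Section 4.1 sits awkwardly beside that. Use of faricimab in the fellow eye is plausible, since Protocol Section 4.3.1 refers to its commercial availability and follow-up may outlast the main study.

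Part of this stands. The rule has no stated rationale, and Section 4.8 is silent about it. But the fact that the columns may already differ is no argument for adding a further difference. The tension with the real-world aim concerns the paired comparison as much as the study-eye table, and there the exclusion protects the contrast: an eye that has received faricimab is no longer an eye without it. As for Section 4.8, the rule is set out openly in Section 4.1 with every therapy named, SAP Section 3 says that Section 4 will specify the data points used, and SAP Section 1 says that the SAP supersedes the protocol's analysis plan. Since the protocol is silent on data after such use, it is arguable whether filling that gap is a change that Section 4.8 has to list.

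**Conclusion.** No change to the plan is needed. The observation is accurate: the study-eye exclusion adds nothing to the paired test, it can reduce n in up to 6 descriptive summaries, and Section 4.8 does not mention it. But 0 of 12 paired tests depend on it. The choice lies between a slightly larger study-eye n and not letting this event separate the patients behind the two columns, and for an endpoint defined as a comparison between eyes the SAP's choice is defensible. Listing the rule in Section 4.8, or giving the number of patients affected in the study report, would be tidy but would leave the results and conclusion equally sound.

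This rests on two assumptions. The first is that the endpoint is the between-eye comparison of SAP Section 1.1 and Protocol Section 2.1.1. The second is that few patients are affected. The documents give no count, but the paired result is the same whatever the number.
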